Up to 40 patients total may be recruited to have a total of 30 analyzable patients. This includes a buffer of up to 10 patients to replace any that do not complete the study. Children will be enrolled from two large pediatric practices. Informed consent will be obtained from a parent or legal guardian.

This age group was chosen because of the high incidence of URI. Children of this age bear the highest burden of URI and its complications.

Health Link IT will be asked to run a bi-monthly list of potential subjects who are greater than 12 months-36 months of age and have a clinic appointment for a well-child clinic visit at 20 S Park Pediatrics or West Towne Pediatrics. A letter of introduction will be signed by the primary pediatrician and mailed to each family. The research nurse will put a reminder note on the door after the child is roomed at the clinic to remind the pediatrician that this is a potential subject for the study. The reminder note will have inclusion/exclusion criteria and a brief synopsis of study participation.

During the visit, the clinic staff or pediatrician will ask the family if they are interested in learning more about the study. If yes, the study nurse will be summoned at the end of the clinic visit to discuss the study with the family.

All children will receive a daily dose of probiotic (10⁹ cfu of *L.acidophilus* NCFM and *B. lactis*, Bi-07), a commercially available probiotic. The product is stable at room temperature for 6 months. *L. acidophilus* NFCM and *B. lactis-07* are classified by the FDA as a Generally Recognized as Safe (GRAS) food ingredient. This particular combination probiotic was chosen because it has shown efficacy in published clinical trials for URI in children and adults. Parents will give probiotic in 1 ounce of milk or water once a day for 30 days in an open label fashion.

A baseline blood sample (5-10 ml) will be obtained for immunologic studies (see below). If the child is having standard of care lab work done, the research staff will accompany the family to the lab with the research kit. Parents will be texted every week to determine if any illnesses have occurred in the interval and if the child has received any antimicrobials. In addition, a daily diary will be completed recording the presence of respiratory or gastrointestinal symptoms or signs and the administration of the investigational product. This will suffice to record illness events or any adverse events experienced by the participants.

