The study product will be supplied by DuPontTM Danisco[®] in individual sachets containing of 5 x 10⁹ *L*. acidophilus and 5 x 10⁹ *B*. lactis. The contents of one sachet will be added to 1 ounce of milk or water each morning. The product will be packaged and labelled by Danisco and shipped to the research pharmacy of the University of Wisconsin where it will be stored in the refrigerator. A 36 supply will be given to each subject.

Subjects will ingest one sachet daily in 1 ounce of milk or water.

There is no randomization. All patients receive the study product. The research pharmacy and study coordinators will be responsible for reconciling the product.

Laboratory Testing

Blood samples: All subjects will undergo blood draws at Visits 1 and 2. The pediatric research staff will obtain the blood either at a clinic visit or a home visit. The tubes will be transported by the research staff to the UW Research Lab located in WIMR ([name]). Total blood volume will be between 5-10 mL following the maximum allowable amount in the AFCH guideline. The initial processing of blood samples will be done in [name] lab. Cytokine analysis will be measured fee-for-service by RBM Myriad (Austin,TX).

Nasopharyngeal swabs: All subjects will have a nasopharyngeal swab obtained at Visits 1 and 2. The swabs will be placed into RNA Later medium and frozen within 7 days of collection in the pediatric -80C freezer located in H4/4. Nasopharyngeal swab samples for assessment of the nasopharyngeal microbiome will be collected at enrollment and at the follow-up visit. (Copan Diagnostics, Inc. Murrieta California). The soft strands of nylon on the swab result in tremendously improved patient comfort and efficiency in specimen collection. The velvet brush-like texture collects liquid by capillarity and rapidly and efficiently dislodges cells, providing an optimal approach to sampling for this study. The swab is inserted into the nostril along the floor of the nasal cavity until the posterior wall is reached. The swab is held in place for 5 seconds while rotating gently. Stool sample collection kits will be given to parents at the start of the study. Stools will be collected at study entry and after 30 days. Stool samples will be frozen at -80C until analysis.

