Immunoprofiling of antigen stimulated blood. The TruCulture system(Myriad RBM) will be used to assess immune function pre and post probiotic supplementation.⁴³ This is a syringe-based device designed for point of care use. The tubes contain 1 ml of cell culture medium which will include resiquimod R848 and possibly other stimulants. R848 is a synthetic agonist of TLR7 and TLR8. In addition a control (null) tube will contain only cell culture medium. One ml of whole blood will be mixed with medium in each tube and incubated at 37 C in a dry heat-block for 24-48 hours. After incubation, cells are separated by a valve separator component. The supernatant is stored at -20 C until analysis. The cellular component will be banked for future studies. Cytokine levels on supernatants will be sent to and measured by a commercial laboratory (RBM Myriad-Austin, TX). Measured cytokines will include GCSF, IL-2, IL-3, IL-5, IL-6, IL-7, IL-8,IL-10, MIP-1 alpha and beta, MCP-1, TNF-alpha, TNF-beta, IFN-alpha, IP-10 and others. [name] lab will perform initial processing of blood specimens. Cytokine determination will be performed fee-for-service by RBM Myriad (Austin,TX).

Data analysis, interpretation, and expected outcome: The primary endpoint for this aim is determination of quantitative responses of whole blood leukocytes to varied agonists. We expect that probiotic exposure will be associated with enhanced production of IL-10TNF α and IFN α . The changes found will be attributed to the probiotic intervention since precision testing using this assay by others has demonstrated good sample replication⁴³.

Specific Aim 2: To demonstrate the impact of probiotic supplementation on the NP and fecal microbiome.

The impact of probiotic consumption on the NP and fecal microbiota will be determined by assessing study subjects at initiation and conclusion of the study. We hypothesize that the administration of probiotic will be associated with an increase in the richness and diversity of the microbiota after 1 month of probiotic supplementation as measured by Shannon-Weiner and unweighted UniFrac 1 indexes.

Methods: NP and stool samples will be collected immediately and stored at -80 °C until analysis. Total bacterial DNA will be extracted from stool and NP samples as described.^{44,45} The 16S V1-V2 region will be amplified using primers containing sample-specific barcodes and sequenced. This analysis will be performed by the [name] laboratory at UCSF.

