Data analysis, interpretation, and expected outcome: Data analysis will be performed in QIIME with Operational Taxonomic Units (OTUs) chosen based upon 97% sequence similarity. Statistical differences between treatment arms and between samples collected pre- and post-administration of probiotic will be examined using the Monte-Carlo test in R with the Benjamini-Hochberg procedure applied to control the false discovery rate.⁴⁶ We hypothesize that the administration of probiotic will be associated with a significant increase in the richness and diversity of microbiota as measured by Shannon-Weiner and unweighted UniFrac 1 indexes.

Statistical Considerations (Aim 1 and 2): *Endpoints*: The primary outcome will include innate immune cell function parameters, adaptive and NK cell function parameters, and Treg cell number/function parameters.

Sample Size and Power Calculation: A sample size of 30 subjects is proposed for this pilot study. In our previous study involving intracellular cytokine and surface staining of PBMCs samples, the observed effect sizes for evaluating differences in the primary monocytes and mDCs parameters between various subgroups ranged from 0.52 to 1.68. The proposed sample size of 30 subjects is adequate for detecting anticipated moderate (0.5-0.8) to large (>0.8) effect sizes for the changes from the baseline to the one month follow-up assessment in the primary innate immune cell function cell function parameters with sufficient power. The following table shows that attainable power levels for detecting moderate effect sizes (ES) ranging form 0.5 to 0.8 using a two-sided paired t-test with a false-discovery rate (FDR) of 0.05, assuming a sample size of 30 subjects with an attrition rate of 10% and a panel of 30 target parameters where the true mean differences (D) exceed the effect size in K=10 to 20 parameters.

Table: Attainable power levels for detecting moderate to large effect sizes with proposed sample size of 30 subjects

	Effe bas	Effect size for change in outcome parameters from baseline to the 3-month follow-up assessment										
		0.5		0.6			0.7			0.8		
K (#D>ES)	10	15	20	10	15	20	10	15	20	10	15	20
Power (%)	55	73	89	78	89	96	91	96	99	99	99	99

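### Aim 2 has no stated step to separate the two swallowed organisms from the child's own bacteria, so the product itself can move the before-after stool comparison.

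*Protocol*

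**What the plan says.** Specific Aim 2 of the protocol asks what supplementation does to the nasopharyngeal and fecal microbiome. Its Methods paragraph states "Total bacterial DNA will be extracted from stool and NP samples". The data-analysis paragraph that follows names QIIME with "Operational Taxonomic Units (OTUs) chosen based upon 97% sequence similarity", and says that differences "between samples collected pre- and post-administration of probiotic will be examined using the Monte-Carlo test in R", with Benjamini-Hochberg control of the false discovery rate. The expected result has a direction: "an increase in the richness and diversity of the microbiota after 1 month of probiotic supplementation", repeated in the data-analysis paragraph as an "increase in the richness and diversity of microbiota as measured by Shannon-Weiner and unweighted UniFrac 1 indexes".

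The design has one arm: "There is no randomization. All patients receive the study product" (Probiotics section). On intake, the same section says "Subjects will ingest one sachet daily in 1 ounce of milk or water", each sachet holding two organisms, and Research Design and Methods has parents give it "once a day for 30 days in an open label fashion". Laboratory Testing places the second stool after 30 days. The Table of Study Procedures puts Visit 2 at Day 27-38. No washout is stated. The Exclusion Criteria remove children who are taking probiotics or took them in the two weeks before entry.

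The protocol does not say whether reads of the two administered organisms are kept, removed or reported separately. The Probiotics section does say that both strains can be identified genetically.

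**The concern.** The entry criteria keep recent probiotic exposure out of the first stool, and the schedule builds it into the second. Extracting all bacterial DNA means that product cells, live or dead, are sequenced with everything else. An OTU that appears only because the child swallowed it then counts in the same way as a resident OTU.

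What is at stake is the meaning of a positive Aim 2 result. The Background section argues that changes in the microbial environment alter immune function and the frequency of respiratory infection. Recovering the product in stool is weak evidence that the child's own community has changed, and the analysis as described would not tell the two apart. The planned subgroups by compliance could add to the confusion, since better compliers are more likely to have detectable product. The control group that the protocol foresees for a later expansion would not remove the problem, because only treated children would receive the organisms.

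**Working it through.** The protocol states no power, effect size, baseline or SD for any microbiome measure, so there is no figure of its own to reproduce. The check asks what the product alone can do to each measure if the resident community does not change.

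**Inputs from the protocol:** two organisms, daily dosing, second stool at Day 27-38, 97% OTUs, n = 30. **Assumed:** baseline OTU count, SD of change, baseline Shannon value H, and the product's share p of stool reads.

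**Richness.** Two organisms add at most two OTUs. Relative to an assumed baseline of 30, 100 or 200 OTUs, that is 2/30 = 6.7%, 2/100 = 2% or 2/200 = 1%.

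For the chance that this alone looks significant, take a two-sided paired t-test at 5% with n = 30, effect size ES = gain/SD of change and noncentrality ES × √30:

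| Mean gain | SD of change (assumed) | ES | Noncentrality | Rejection probability |
|---|---|---|---|---|
| 2 OTUs | 5 | 0.40 | 2.19 | 56.3% |
| 2 OTUs | 10 | 0.20 | 1.10 | 18.5% |
| 2 OTUs | 20 | 0.10 | 0.55 | 8.3% |
| 1 OTU | 5 | 0.20 | 1.10 | 18.5% |
| 1 OTU | 10 | 0.10 | 0.55 | 8.3% |
| 1 OTU | 20 | 0.05 | 0.27 | 5.8% |

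With 27 children, after the 10% attrition used in the protocol's power section, the two-OTU figures are 51.7%, 17.0% and 7.9%. All are unadjusted. Benjamini-Hochberg adjusted p-values are never below the raw ones, so adjustment can only lower these rates.

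**Shannon.** Suppose two product OTUs, absent at baseline, share a fraction p of reads equally and the resident proportions are otherwise unchanged. Then

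change = h(p) + p ln 2 − pH, with h(p) = −p ln p − (1−p) ln(1−p).

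At H = 3:
- p = 10%: 0.325 + 0.069 − 0.300 = +0.09
- p = 30%: 0.611 + 0.208 − 0.900 = −0.08

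The largest possible gain is ln(1 + 2e^(−H)): 0.24, 0.15, 0.095 and 0.06 at H = 2.0, 2.5, 3.0 and 3.5. Shannon falls once the product exceeds about 53%, 36%, 24% and 15% of reads respectively. A shift of +0.1 at n = 30 would reach unadjusted p<0.05 in 75%, 42% or 19% of trials for an assumed SD of change of 0.2, 0.3 or 0.5.

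**Unweighted UniFrac.** This is the branch length found in only one of two samples, U, divided by the total branch length, T. A product OTU present only afterwards adds its own branch length b to both. Since (U + b)/(T + b) > U/T whenever U < T and b > 0, the pre-post distance grows. A distance between two samples does not say which one is more diverse.

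**The case against.** The strongest reply is that this rests on silence. The protocol does not say that product reads are kept, and taxon filtering is a detail that an unseen SAP or laboratory plan may hold. A reader might infer that the plan has chosen to count the product as resident flora; the text does not support that. What remains is that the protocol already fixes the OTU definition, test, error control, indices and expected direction, and that sequence has no step separating product from resident bacteria.

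A reader might also infer that every child's diversity will rise spuriously. That does not follow:
- The richness gain is capped at two OTUs. It is smaller or nil if a product OTU is already present or a resident shares it.
- Shannon can fall, and UniFrac has no direction of diversity. No separate richness index is named.
- Compliance will vary. The 30-day course, the Day 27-38 window and a supply figure of 36 do not settle whether intake continues to the visit, so some product may have cleared. Those passages need to be reconciled.
- The mechanism concerns stool and does not obviously carry over to nasopharyngeal swabs.

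Third, Aim 2 asks about the microbiome, and the administered organisms may fairly be counted as part of it. That is a good reason to keep the all-OTU analysis. It does not license describing the result as a change in the child's own flora. Finally, filtering remains possible on the existing data at any time. That is correct, and it keeps the cost low.

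**Conclusion.** The concern holds in a limited form. With the stated pipeline and timing, detection of the two administered organisms can add up to two OTUs, shift Shannon in either direction and add pre-post UniFrac distance with no change in resident bacteria. How much is unknown. The richness figures of 56.3%, 18.5% and 8.3% need a gain of two OTUs in all 30 children, assumed SDs of change of 5, 10 and 20, and an unadjusted paired t-test; Aim 2 names a Monte-Carlo test with false-discovery control. At the larger SDs, or with a mean gain of one OTU, several figures lie close to the nominal 5%.

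It would go too far to say that a positive Aim 2 result must be an artefact. The documents show only that it could be partly one, and that the analysis as described would not reveal it. The primary outcomes are immune parameters and the study is an exploratory pilot, so this is a cheap improvement and not an error in a stated figure.

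**What to change.** For stool, state in the Aim 2 analysis that:
- OTUs assigned to the two administered species are reported separately, before and after dosing.
- A named richness index, Shannon and unweighted UniFrac are each computed twice: on all OTUs, and with those OTUs removed from both the pre and post samples.
- A result is described as a change in the child's own microbiota only if it holds in the filtered version.
- UniFrac is interpreted as a measure of compositional change, not of increased diversity.

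Removing the OTUs from both samples sets the product's direct contribution to zero by construction. The cost is one extra run of the same pipeline on existing data, with no new samples. The downside is that resident OTUs of the same two species are removed too, which is why the all-OTU version should be reported alongside.

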Hence, under various scenarios, a moderate effect size for the changes in the target parameters will be detected with 55-99% power while a large effect size will be detected >99% power. In summary, the proposed sample size of 30 subjects is sufficient for detecting differences in the primary target parameters which will provide preliminary data for conducting a larger validation study. It is unknown whether this effect size has clinical relevance at this time in terms of prevention of infection. We hope to test this in a larger controlled trial.

Statistical Analysis Plan: All outcome parameters will be summarized using standard descriptive statistics in terms of means, standard deviations, medians and ranges. Absolute and percentage changes from the baseline to the month 3 assessment will be calculated and evaluated using a paired t-test or nonparametric Wilcoxon signed rank test. The Benjamini-Hochberg method will be utilized to control the false discovery rate. Subgroup analyses will be conducted by compliance rates (at least 50%, 75% or 90% compliant). Pearson or nonparametric Spearman's rank correlation analyses will be conducted to evaluate associations of changes between outcome parameters. These analyses will be considered exploratory.

Data and Record Keeping

The master subject key will be maintained by the research staff and will be stored in an excel document on the Department of Pediatrics password-secure server. The code will be a unique number. The coded data will be maintained by the research staff and will be stored in a locked drawer in the research staff's locked office.

The excel file containing the data collection variables will be stored on the Department of Pediatrics password-

secured server. Only research staff will have access to this file. The file will contain the unique subject code but will not have any identifiers such as name, date of birth, or MRN#.

Specimens sent to UCSF will include a de-identified specimen number. Specimens sent back from UCSF will include microbiome profiles linked to the same de-identified specimen number. Specimens sent to RBM Myriad will include a de-identified specimen number. Specimens sent back from RBM Myriad will include cytokine profiles linked to the same de-identified specimen number.

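### The power table assumes, without justification, that 10 to 20 of 30 parameters truly change; with fewer true changes, average power under the planned Benjamini-Hochberg analysis is below every column shown.

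*Protocol*

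**What the plan says.** In the Protocol, Sample Size and Power Calculation, power is computed "using a two-sided paired t-test with a false-discovery rate (FDR) of 0.05", for "a panel of 30 target parameters", and for "moderate effect sizes (ES) ranging form 0.5 to 0.8". The calculation runs "assuming a sample size of 30 subjects with an attrition rate of 10" per cent, and supposes that "true mean differences (D) exceed the effect size in K=10 to 20 parameters". The table has columns for K = 10, 15 and 20 only. The text below it reads off 55-99% power for moderate effects, under various scenarios, and then calls 30 subjects sufficient.

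The Statistical Analysis Plan paragraph fixes the multiplicity method: "The Benjamini-Hochberg method will be utilized to control the false discovery rate".

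Under Specific Aim 1 (data analysis, interpretation and expected outcome), the expectation for the cytokine assay is: "We expect that probiotic exposure will be associated with enhanced production of" IL-10, TNF-alpha and IFN-alpha. The same section fixes one stimulant, R848, and leaves others open. Background and Significance and the Study Objectives add a hypothesis of increased number and function of pDC and Treg cells, without saying how many parameters that makes.

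On evaluable numbers, the enrolment text says "Up to 40 patients total may be recruited to have a total of 30 analyzable patients".

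**The concern.** Under a false-discovery-rate procedure, power for one parameter depends on how many other parameters truly change. Each true rejection loosens the threshold for the next. Assuming that 10/30 = 33% to 20/30 = 67% of the panel truly changes is therefore a strong input, and it drives the printed figures. The Protocol neither justifies the range nor shows what happens below it, although the only cytokines it expects to move are three.

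The figure is relied on. Background and Significance says that markers with a significant change will become the primary outcomes of the later controlled trial, with TNF-alpha as the example. If power per true effect is overstated, a marker that does not reach significance will be read as more clearly unaffected than the data allow.

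**Working it through.** **Inputs (all Protocol).** Two-sided paired t-test, FDR f = 0.05, m = 30, K = 10/15/20, ES 0.5 to 0.8. The power text gives 30 subjects with 10% attrition: 30 × 0.9 = 27 evaluable. The enrolment text gives 30 analyzable. I show both.

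**Meaning of power.** The Protocol does not define it. I take average power per truly changed parameter, and ES as mean change divided by the SD of the change. The t statistic then has noncentrality ES × √n (at ES 0.5: 2.74 for n=30, 2.60 for n=27).

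**Step 1: the plan's own table.** The closest two-sided reproduction uses the marginal-FDR formula with the number of null parameters known, solved with the noncentral-t power π:

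α* = f·K·π / [(m − K)(1 − f)]

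For K=10, ES 0.5, n=30: α* = 0.05 × 10 × 0.565 / (20 × 0.95) = 0.0149, and the paired-t power at that level is 56.5% (printed: 55%). At n=30 this matches 11 of 12 cells within 2 points; the exception is ES 0.5, K=20 (83% against 89%). At n=27 it matches 3 of 12 (ES 0.5: 48/64/78% against 55/73/89%). The table therefore looks like n=30 without the stated attrition.

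**Step 2: the planned procedure at the plan's own K.** Benjamini-Hochberg does not know the number of nulls. With independent parameters it holds the FDR at f(m − K)/m, which at K=10 is 0.05 × 20/30 = 0.033, so it is stricter than the formula in Step 1. I simulated it: independent parameters, step-up at 5%, share of true effects rejected.

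**Step 3: smaller K, same simulation.**

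| Average power (%), ES 0.5/0.6/0.7/0.8 | n=30 | n=27 |
|---|---|---|
| Printed table, K=10 | 55/78/91/99 | – |
| BH, K=10 | 49/73/89/96 | 41/66/84/93 |
| BH, K=6 | 40/65/84/94 | 33/57/77/90 |
| BH, K=3 | 33/55/76/89 | 27/47/68/84 |

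Separate runs differ by about one point per cell. Pairwise correlation of 0.5 changes little (K=3, n=27: 27/46/66/83%).

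**Step 4: splitting the K=3 gap at n=30.**
- Total against the printed K=10 column: 55−33, 78−55, 91−76, 99−89 = 22/23/15/10 points.
- Due to K itself (BH, K=10 to K=3): 49−33, 73−55, 89−76, 96−89 = 16/18/13/7 points.
- Due to the table being too high for BH at K=10: the remaining 6/5/2/3 points.

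At n=27 the total is 28/31/23/15 points, of which 14/19/16/9 come from K.

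**Step 5: is average power the right reading?** At K=10, n=30, ES 0.5, the simulated chance of detecting at least one true effect is about 98%, and of detecting all ten below 1%. The printed 55% fits neither, so the table is average power or close to it.

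**The case against.** **K=3 is not stated as a maximum.** A reader might infer that the power table contradicts the Protocol's own hypothesis. The text does not go that far. It expects three cytokines to rise but does not say that only those three change. The endpoint refers to varied agonists, and the pDC and Treg hypotheses and the adaptive and NK parameters could add to K. Three cytokines under two stimulants already make six. This stands, and is why K=6 is shown. It does not rescue the table: K=9 gives about 47/72/88/96% at n=30, still under 55/78/91/99%.

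**The 15 named cytokines.** A reader might infer that K=20 is impossible because only 15 cytokines are named. That mixes units. The table counts parameters, a cytokine can count once per tube condition, and the list is left open.

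**Missing a moderate effect.** A reader might infer that the study would probably miss a moderate effect. The Protocol's moderate range is 0.5 to 0.8. At K=3 average power is below one half only at ES 0.5, and at ES 0.6 if n=27. The chance of finding at least one of the three is about 62/85/97/99% at n=30 and 54/78/93/99% at n=27.

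**The assumption is disclosed, in an exploratory pilot.** K is stated and the power range is tied to scenarios. That makes this an optimistic, unjustified range rather than a hidden one. The sufficiency conclusion, however, carries no such condition, and significance is the rule for choosing later outcomes.

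**A separate family for the three cytokines.** This should not be read as a required correction. It narrows a screening study, and its attractive power of 72/88/96/99% at n=30 assumes that all three change. If only one does, it is about 59/77/90/96%.

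**Conclusion.** The point holds as an unsupported assumption behind a relied-on figure. The range K = 10 to 20 has no basis in the text, no smaller K is shown, and average power under the planned Benjamini-Hochberg analysis is below the printed columns at the same effect size for every K under 10. For K between 3 and 6 it runs from about 33% to 94% with 30 evaluable children and from about 27% to 90% with 27, against the stated 55-99%. The shortfall is largest at ES 0.5 to 0.6 and modest at 0.8. Part of it is not about K: the table is somewhat high for this procedure even at K=10.

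The figures assume a common effect size across the true changes, normally distributed changes, independent parameters, a 30-parameter panel and power as average power per true effect. The documents do not establish K=3 as the true number, and the conclusion does not need it.

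**What to change.** In Sample Size and Power Calculation:

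1. Add low-K entries, for example K=3 and K=6, and compute all entries, including K = 10 to 20, for the planned Benjamini-Hochberg procedure. If 10 to 20 stays as a main scenario, say why.
2. State the evaluable n used (27 or 30) and that power means average power per true effect.
3. Replace the 55-99% statement and the sufficiency conclusion with the resulting lower range.

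Optional, at the sponsor's choice: a separate family for IL-10, TNF-alpha and IFN-alpha. If it is adopted, show its power at n=30 both when all three change (72/88/96/99%) and when only one does (about 59/77/90/96%).

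Items 1 to 3 cost wording and a short recalculation, with no added children, samples or assays. The optional family has a real price: the remaining parameters become secondary.
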